#### **4.2.11 Long-term Follow-up Visit (Month 24 ± 2 month)**

Subjects who complete 6-month visit and accept the long-term follow-up visit will visit the clinical site for the following assessments/procedures:

- The following questionnaires/procedures will be completed: WOMAC (see Appendix 3), VAS (see Appendix 4), Lysholm scale (see Appendix 5), KOOS (see Appendix 6), IKDC (see Appendix 7), and RAND-36 (see Appendix 8).
- Collect records of treatments and medications since the last visit.
- Measure vital signs (sitting blood pressure, pulse, breathing, and temperature) and weight.
- Perform a complete physical examination.
- Perform MRI measurement (Please follow the collection instruction separately provided by the sponsor).

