**Secondary Endpoints:**  
1) JointStem group vs. positive control group  
① Change of WOMAC score from baseline at Month 6  
② Change of VAS score from baseline at Month 6  
③ Change of KOOS from baseline at Month 6  
④ Change of Lysholm Knee Scoring Scale from baseline at Month 6  
⑤ Change of IKDC from baseline at Month 6  
⑥ Change of RAND-36 Score from baseline at Month 6  
2) JointStem group  
① Change of WOMAC score from baseline at Months 9 and 12  
② Change of VAS score from baseline at Months 9 and 12  
③ Comparison of MRI improvement evaluations between at Month 6 and at Month 12  
④ Change of Lysholm Knee Scoring Scale from baseline at Months 6, 9 and 12  
⑤ Change of KOOS from baseline at Months 6, 9 and 12

- ⑥ Change of IKDC from baseline at Months 6, 9 and 12
- ⑦ Change of RAND-36 Score from baseline at Months 6, 9 and 12
- 3) Incidence of adverse events and laboratory abnormalities

**Exploratory Endpoints:** Analysis of all efficacy scales and MRI results and the history of treatments and medications following 2 years after injection for all subjects who are injected and complete 6-month follow-up visit

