### **3.3 Removal of Subjects from Study**

Subjects may be withdrawn from the study for the following reasons:

- At their own request or at the request of their legally acceptable representative
- If, in the investigator's opinion, continuation in the study would be detrimental to the subject's well-being
- At the specific request of the sponsor

Also, subjects must be withdrawn for the following reasons:

- A significant violation of the protocol, as determined by the sponsor or the investigator
- Highly significant abnormalities in the laboratory results (Highly significant abnormalities generally follow lab related exclusion criteria, but a PI can determine the high significance on any abnormalities for the safety of subject)
- Use of any other investigational drugs (including placebo)
- Subjects enrolled in the current trial but taking any prohibited medication/therapy stated in the inclusion/exclusion criteria that, in the investigator's opinion, will interfere with the study outcome.
- Subject enrolled in the current trial but having a baby

If a subject prematurely withdraws from the study, the subject must return to the clinical site for the early termination visit. In all cases, the reason for withdrawal must be recorded in the electronic Case Report Form (eCRF) and in the subject's medical records.

Contact will be maintained with subjects who are removed due to an adverse event (AE) until it has been resolved or stabilized, and the information will be documented in the eCRF and in the subject's medical records.

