#### **3.5.7 Prior and Concomitant Treatments**

If the use of any concomitant treatment(s) becomes necessary, the treatment(s) must be recorded in the eCRF, including the name of the drug or treatment, dose, route of administration, date and time of the treatment, and indication. In the event that concomitant medication is administered, the

principal investigator or qualified sub-investigator must assess the subject's eligibility of continuing the participation in the study.

The following medications/therapies are not allowed to be taken/used by subjects enrolled in this study during the trial (by 6-month follow-up visit):

- Any pain medication for osteoarthritis except rescue medication (< acetaminophen 3.25 g per day or narcotic pain medications per investigator discretion in the case all other pain control measures have failed. Any pain medication other than acetaminophen 3.25g should only be used as last resort and only for a very limited time until symptoms can be controlled by more conservative methods).
- Any other injections or invasive procedures (including intra-articular injections) in the affected joint
- Any investigational drug (including placebo)
- Any therapy that may affect osteoarthritis, in the judgment of the investigator
- Lidocaine or other numbing agents while making the injection

After the completion of the 6-month follow-up visit, subjects may take pain medication for osteoarthritis and all medications will be tracked and recorded. Until the subjects complete the 12-month follow-up visit, any other treatments/therapies including surgeries (e.g. artificial joint replacement surgery) that, in the judgment of the investigator, affect the assessment of osteoarthritis will be prohibited.

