## **6.4 Long-term Follow-up Analysis**

All efficacy variables and the history of treatments and medications, which are measured at a long-term follow-up visit (24 months after injection) will be analyzed between treatment groups to see any long-term effects of JointStem. Also, MRI results of long-term follow-up visit will be compared to previous MRI results to see any long-term effects of JointStem. The details of this long-term follow-up analysis will be presented in the statistical analysis plan.

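### The Month 24 comparison of treatment history is limited to Month 6 completers, so it may leave out some subjects because they needed other knee treatment early

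*Protocol*

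**What the plan says.** **Who enters Month 24.** Protocol 4.2.11 states: "Subjects who complete 6-month visit and accept the long-term follow-up visit will visit the clinical site". The synopsis (Study Design) and Section 3.5.3 set the same condition. The synopsis entry for exploratory endpoints defines the analysed population likewise, "for all subjects who are injected and complete 6-month follow-up visit".

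**What is compared.** The Month 24 data are all efficacy scales, MRI, and the history of treatments and medications. Section 6.4 says that the scales and the treatment history "will be analyzed between treatment groups to see any long-term effects of JointStem". It leaves the details to the SAP. The SAP has no Month 24 analysis, and its schedule (Table 1) ends at Month 12.

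**What happens before Month 6.** Section 3.5.7 lists treatments prohibited up to the Month 6 visit, among them "Any other injections or invasive procedures (including intra-articular injections) in the affected joint". Section 3.3 requires withdrawal of subjects "taking any prohibited medication/therapy stated in the inclusion/exclusion criteria that, in the investigator's opinion, will interfere with the study outcome". It also requires withdrawal for a significant protocol violation, as determined by the sponsor or the investigator. Under Section 4.2.9 the site tries to arrange one early termination visit for a subject who leaves before Month 6. Section 3.3 provides for later contact only after removal for an adverse event, until the event resolves or stabilizes.

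**The concern.** Treatment history at Month 24 is meant to show whether subjects went on to need something else for the knee. A subject who has another injection or a procedure in that knee at, say, Month 3 has already had this outcome. If the treatment leads to withdrawal, the subject never completes Visit 6, is not invited at Month 24, and falls outside the endpoint population. Having the event early can thus remove a subject from the analysis of the event.

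This is selection on something that happens after randomization and is tied to the outcome being compared. An arm that loses subjects in this way would show too low a rate of other treatment. If the arms lose different proportions, the difference between them is distorted. The point concerns the Month 24 entry rule; it is separate from how a missing Month 6 score is handled.

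**Working it through.** **Step 1: does anything bring these subjects back?**

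| Stage | Protocol section | Effect |
|---|---|---|
| Other knee injection or procedure before Month 6 | 3.5.7 | Prohibited |
| Judged to interfere, or to be a significant violation | 3.3 | Must be withdrawn |
| After withdrawal | 4.2.9 | One early termination visit |
| Month 24 invitation | Synopsis, 3.5.3, 4.2.11 | Only after a completed Month 6 visit |
| Endpoint population | Synopsis | Injected and completed Month 6 |
| Between-group comparison | 3.6.1, 6.4 | No rule for subjects who left early |

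Nothing in either document returns them to the comparison.

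**Step 2: inputs.** The planned arm sizes are 20 and 10 (Protocol 6.2), which is 30 split 2:1. There is no stated figure for this issue to reproduce. The two quantities that drive the bias are not in the documents and are assumed here:

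- w = share of an arm withdrawn before Month 6 because of other treatment;
- q = rate of other treatment by Month 24 among Month 6 completers.

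For simplicity, nobody leaves for another reason and all completers accept the visit.

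**Step 3: formula.**

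- Rate as the plan would estimate it: q
- Rate among all injected subjects: w + (1 − w)q
- Understatement: w + (1 − w)q − q = w(1 − q)

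**Step 4: one arm of 20.** Suppose 3 are withdrawn early for other treatment and 5 of the remaining 17 have other treatment later. The plan's rate is 5/17 = 29.4%. The rate among all injected subjects is (3 + 5)/20 = 40.0%. Keeping q = 0.294 and varying the number k withdrawn, so that w = k/20:

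| k of 20 | Plan's rate | All injected | Understatement |
|---|---|---|---|
| 0 | 29.4% | 29.4% | 0 points |
| 1 | 29.4% | 32.9% | 3.5 points |
| 2 | 29.4% | 36.5% | 7.1 points |
| 3 | 29.4% | 40.0% | 10.6 points |
| 4 | 29.4% | 43.5% | 14.1 points |

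Over a wider range, w from 10% to 30% and q from 20% to 50%, the understatement runs from 0.1 × 0.5 = 5 points to 0.3 × 0.8 = 24 points.

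**Step 5: between arms.** Take q = 30% in both arms, so completers show no difference.

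- 2 of 20 JointStem and 3 of 10 control subjects withdrawn: 0.1 + 0.9 × 0.3 = 37% against 0.3 + 0.7 × 0.3 = 51%. A 14-point difference in favour of JointStem is missed.
- 6 of 20 JointStem and 1 of 10 control subjects withdrawn: 51% against 37%. A 14-point difference against JointStem is missed.

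In the control arm a single withdrawal among 10 moves the rate by 0.1 × 0.7 = 7 points.

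**The case against.** A reader might infer that anyone who takes another treatment before Month 6 is automatically withdrawn and lost. The documents do not support this. Section 3.3 turns on a judgement by the investigator or sponsor, and its medication clause refers to treatment named in the eligibility criteria. The injection and surgery exclusions in 3.2.2 look back from Screening or Visit 2, so a later injection might lead to withdrawal only as a significant violation. Section 3.5.7 permits acetaminophen below its stated limit and also "narcotic pain medications per investigator discretion in the case all other pain control measures have failed". Some subjects who need more treatment early will therefore complete Month 6 and be invited. The loss is of some early users, not necessarily all.

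A reader might also infer that the rule favours JointStem. Step 5 shows that the sign depends on which arm loses more, and the documents do not say.

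Nor are early failures hidden. Reasons for withdrawal and concomitant treatments go into the eCRF (3.3, 3.5.7), medication changes and questionnaires are collected at early termination (4.2.9), and SAP 3.1 tabulates reasons for withdrawal by treatment. This stands, but those subjects remain outside the Month 24 comparison. It mainly makes the correction cheaper.

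The population is openly stated, the endpoint is exploratory, attendance is voluntary, and the trial is a proof-of-concept study without a formal sample size calculation. That lowers the priority without removing the selection.

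Two limits survive any change to the entry rule. Subjects may still decline Month 24. In addition, 3.5.7 restricts other treatments until the 12-month visit, while control subjects have no scheduled visit between Month 6 and Month 24 (3.5.8), so treatment history may not be fully comparable between arms even with everyone in the denominator.

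**Conclusion.** The point holds as a possible selection bias in an exploratory comparison. As written, the between-group analysis of treatment history depends on completing Month 6, and needing other knee treatment can prevent completion. The illustrative understatement is about 4 to 14 percentage points for 1 to 4 such withdrawals among 20 subjects at a later rate of 29%. It is zero if there are none. These figures rest on assumed withdrawal and later-treatment rates. The direction of any bias between arms cannot be known from the documents. No primary or secondary endpoint depends on Month 24, so the priority is low.

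**What to change.** **Analysis (Protocol 6.4 and the SAP).** Analyse treatment history among all injected subjects, from injection onwards. Count other knee treatments before Month 6 as events, including those that led to withdrawal. Because the Month 24 record covers only the period since the last visit (3.6.4), join it to the earlier eCRF entries. Report by arm the number withdrawn before Month 6 for this reason and the number whose Month 24 status is unknown. State how scale scores and MRI obtained after other knee treatment will be used.

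**Data collection (synopsis, 3.5.3, 4.2.11).** Offer the Month 24 visit to every injected subject who has not refused further contact. If the visit is declined, collect the treatment record by telephone and send the questionnaires on paper by mail. The VAS is a marked line measured in millimetres, so it cannot be taken by telephone. MRI is omitted in these cases.

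**Wording.** Section 3.3 refers to treatments named in the eligibility criteria, while 3.5.7 has its own, fuller list. The two must be reconciled so that it is clear which early treatments lead to withdrawal.

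**Cost.** A short amendment, a few extra contacts among about 30 subjects, and some incomplete records. The analysis and data-collection changes alter no treatment or withdrawal rule.

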### Schedule of Assessments

	Screen.	Harv.	Treat.	1 st Follow-up				2 nd Follow-Up		Long-term	
Blinding	N/A	Double Blinding							Open 		Follow-up
Visit	1	2	3	4	5	6	ET	7	8	N/A	
Week / Month	W-7	W-5	0	M1	M3	M6	<M6	M9	M12 or Final FU 	M24	
Informed consent	X										
Medical and Medication History	X	X									
Demographic information	X										
Complete physical examination	X		X		X	X	X 	X	X	X	
Vital signs and weight	X	X	X	X	X	X	X	X	X	X	
Hematology, serum chemistry, and urinalysis 	X		X	X	X	X	X 	X	X		
Pregnancy test 	X					X	X 		X		
HIV test for Screening	X										
12-lead ECG	X		X			X	X 		X		
X-ray	X										
Eligibility confirmation	X	X									
Randomization		X									
Liposuction		X									
Injection of final drug product			X								
AE and concomitant medication assessment			X	X	X	X	X	X	X		
Records of Treatment and Medications										X	
MRI scan 	X					X	X 		X	X	
WOMAC			X	X	X	X	X 	X	X	X	
VAS	X		X	X	X	X	X 	X	X	X	
Lysholm			X	X	X	X	X 	X	X	X	
KOOS			X	X	X	X	X 	X	X	X	
IKDC			X	X	X	X	X 	X	X	X	
Quality of Life (RAND-36)			X		X	X	X 	X	X	X	

1. See Appendix 1 for the complete list of laboratory tests
2. Serum pregnancy test is performed for all females of childbearing potential (please refer to the relevant inclusion criteria)
3. May be performed the day of Visit 2 or after due to scheduling or re-scanning.
4. Performed only if the early termination is after V3.
5. Performed only if the early termination is after V4.
6. Performed if the follow-up is discontinued after V6.
7. Only for JointStem group.

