#### **3.5.3 End of Study**

The efficacy results will be analyzed when the last subject completes Visit 6 (6-month follow-up) and this study is finished when the last subject completes Visit 8 (12-month follow-up).

Long-term follow-up visit will be conducted to collect long-term feedbacks (records of medications and treatments) following 2 years after injection for all subjects who complete 6-month visit and accept the long-term follow-up visit.

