## **3.6 Study Endpoints and Variables**

### **3.6.1 Study Endpoints**

The co-primary endpoints are:

Using the following three co-primary efficacy variables, the joint functional improvement of knee joint will be evaluated and gatekeeping procedures will be used for these three hypothesis tests.

- 1) Change of WOMAC score from baseline at Month 6 (JointStem group)
- 2) Change of VAS score from baseline at Month 6 (JointStem group)
- 3) MRI improvement evaluation at Month 6 (JointStem group)

MRI improvement evaluation will be finally analyzed through the following two steps:

- Radiologist will compare and analyze MRI results before and after the administration of IP and write a report for each subject.
- Principal Investigator will evaluate MRI results of subjects as one of three conditions (a: improvement, b: no change, c: progress) based on the radiologist's report stated above.

The secondary endpoints are:

- 1) JointStem group vs. positive control group
  - ① Change of WOMAC score from baseline at Month 6
  - ② Change of VAS score from baseline at Month 6
  - ③ Change of KOOS from baseline at Month 6
  - ④ Change of Lysholm Knee Scoring Scale from baseline at Month 6
  - ⑤ Change of IKDC from baseline at Month 6
  - ⑥ Change of RAND-36 Score from baseline at Month 6
- 2) JointStem group
  - ① Change of WOMAC score from baseline at Months 9 and 12
  - ② Change of VAS score from baseline at Months 9 and 12
  - ③ Comparison of MRI improvement evaluations between at Month 6 and at Months 12
  - ④ Change of Lysholm Knee Scoring Scale from baseline at Months 6, 9 and 12
  - ⑤ Change of KOOS from baseline at Months 6, 9 and 12
  - ⑥ Change of IKDC from baseline at Months 6, 9 and 12
  - ⑦ Change of RAND-36 Score from baseline at Months 6, 9 and 12
- 3) Incidence of adverse events and laboratory abnormalities

Exploratory Endpoint is:

All efficacy variables and the history of treatments and medications, which are measured at a long-term follow-up visit (24 months after injection) will be analyzed between treatment groups to see any long-term effects of JointStem. Also, MRI results of long-term follow-up visit will be compared to previous MRI results to see any long-term effects of JointStem.

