### **3.6.3 Safety Variables**

- Hematology, serum chemistry and urinalysis at Visits 1, 3, 4, 5, 6, 7 and 8 (Screening, Baseline, M1, M3, M6, M9 and M12) or Early Termination (only if the subject is early terminated after Visit 3) or Final Follow-up Visit. See Section Appendix 1 for a complete list of laboratory tests to be done.
- ECG evaluation at Visits 1, 3, 6 and 8 (Screening, Baseline, M6 and M12) or Early Termination (only if the subject is early terminated after Visit 3) or Final Follow-up Up Visit
- Complete physical examination at Visits 1, 3, 5, 6, 7 and 8 (Screening, Baseline, M3, M6, M9 and M12) or Early Termination (only if the subject is early terminated after Visit 3) or Final Follow-up Up Visit
- Vital signs (sitting blood pressure, pulse, breathing, and temperature) and weight will be measured at all visits.
- Data regarding AEs and concomitant medications collected at all visits after randomization

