### **3.6.4 Exploratory Variables**

The following procedures will be performed at 24-month visit ( $\pm 2$  month):

- WOMAC score
- VAS
- MRI scan
- KOOS
- Lysholm Knee Scoring Scale
- IKDC
- RAND-36 score
- Records of treatments and medications since the last visit

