## 7. SAFETY DATA COLLECTION, RECORDING, AND REPORTING

### 7.1 Definitions

#### 7.1.1 Adverse Events

An adverse event is defined in the 21 CFR 312.32(a) as “Adverse event means any untoward medical occurrence associated with the use of a drug in humans, whether or not considered drug related.”

An adverse event (also referred to as an adverse experience) can be any unfavorable and unintended sign (e.g., an abnormal laboratory finding), symptom, or disease temporally associated with the use of a drug, without any judgment about causality. An adverse event can arise from any use of the drug (e.g., off-label use, use in combination with another drug) and from any route of administration, formulation, or dose, including an overdose. Worsening of a pre-existing medical condition (e.g., diabetes, migraine headaches, and gout) after the drug administration should be considered an adverse event if there is either an increase in severity, frequency, or duration of the condition or an association with significantly worse outcomes.

The investigator is responsible for reviewing laboratory test results and determining whether an abnormal value in an individual study subject represents a change from baseline values. Abnormal laboratory findings without clinical significance (based on the investigator's judgment) should not be recorded as adverse events; however, laboratory value changes requiring therapy or adjustment in prior therapy are considered adverse events.

Adverse events will be reviewed continuously throughout the study.

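### Month 24 has no adverse event item, so non-serious events and SAEs not judged related have no scheduled capture after Month 12 (JointStem) or Month 6 (control)

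*Protocol*

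**What the plan says.** Section 3.6.3 of the protocol sets the general rule: "Data regarding AEs and concomitant medications collected at all visits after randomization". It makes no exception. Section 7.1.1 adds: "Adverse events will be reviewed continuously throughout the study".

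Three places define the Month 24 visit:

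- In the Schedule of Assessments, the row "AE and concomitant medication assessment" is marked from Visit 3 through Visit 8, including early termination. It is blank in the long-term column.
- Section 3.6.4 lists the efficacy scales, MRI and "Records of treatments and medications since the last visit".
- Section 4.2.11 lists the questionnaires, vital signs and weight, physical examination, MRI and the instruction "Collect records of treatments and medications since the last visit".

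The aim of the visit is wider than record-keeping. Section 6.4 says the Month 24 data "measured at a long-term follow-up visit (24 months after injection) will be analyzed between treatment groups to see any long-term effects of JointStem", and section 3.6.1 says the same of the exploratory endpoint. Section 6.4 leaves the details to the SAP. The SAP's own schedule (Table 1) has no Month 24 column, and SAP section 7.1 counts treatment-emergent AEs (TEAEs) only up to the end of the study.

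**The concern.** The protocol brings subjects back two years after a cell injection to look for long-term effects, examines and scans them, and asks about treatments and medications, but does not ask what adverse events they have had. The section 3.6.3 rule, read literally, says it should.

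At stake is the late safety record. The study objective is efficacy and safety, and Month 24 is the last planned contact. As written, it can report scores, images and treatment history by arm, but not a list of events with dates, severity, seriousness and relationship to the product. The stretch without scheduled AE questions is also longer for controls than for JointStem subjects.

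**Working it through.** The plan states no figure for this point, so the check sets the texts side by side and sizes the gap from the visit schedule.

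**1. Is the omission complete?** Yes. None of the three places that define Month 24 has an AE item. By contrast, every visit section from injection onward (4.2.3 to 4.2.10, including early termination and final follow-up) has a line for recording AEs. Section 4.2.11 keeps the treatment and medication part of that line and loses the AE part.

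**2. Does the general rule reach Month 24?** On its plain wording it does. The bullet just before it in section 3.6.3 requires vital signs at all visits, and the schedule and section 4.2.11 do measure them at Month 24.

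**3. What does section 7.3 catch?** One sentence collects SAEs from injection to Month 3. The next requires prompt reporting of SAEs during a follow-up period that it does not define. A later one requires SAEs after the end of the study to be reported if thought possibly related. None of these prompts a question at Month 24, and none covers non-serious events.

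**4. Length of the gap.** Inputs: the last scheduled AE visit is Month 12 for JointStem (Visit 8) and Month 6 for controls (Visit 6, protocol section 3.5.8). The Month 24 window is ±2 months (section 4.2.11). Planned numbers are 20 and 10 (section 6.2).

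- JointStem: 24 − 12 = 12 months, 12/24 = 50% of follow-up. With the window: 22 − 12 = 10 to 26 − 12 = 14 months.
- Control: 24 − 6 = 18 months, 18/24 = 75%. With the window: 22 − 6 = 16 to 26 − 6 = 20 months.
- Together: 20 × 12 + 10 × 18 = 240 + 180 = 420 subject-months, out of 30 × 24 = 720. 420/720 = 58%.

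**5. Could there be anything to record?** The documents give no late-event rate, so these risks are assumptions for illustration. The chance of at least one event among n subjects is 1 − (1 − p)^n.

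| Assumed risk p per subject | JointStem, n = 20 | Control, n = 10 |
|---|---|---|
| 5% | 64% | 40% |
| 10% | 88% | 65% |
| 20% | 99% | 89% |

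The information would still be modest. With no events at all, the one-sided 95% upper bound on the risk, 1 − 0.05^(1/n), is 13.9% for n = 20 and 25.9% for n = 10.

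**The case against.** The best defence is that Month 24 lies outside the study proper. Protocol section 3.5.3 ends the study when the last subject has had Visit 8. Month 24 carries no visit number, is attended only by those who accept it, and sits under exploratory rather than safety variables. The synopsis and section 3.5.3 describe its purpose as collecting medication and treatment records. On that view the section 3.6.3 rule means the numbered visits, and the SAP's TEAE cut-off agrees.

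This softens the conflict but does not remove it, because no text states the exception. The end of study is also set by the last subject. Anyone injected more than 24 − 12 = 12 months before that subject would reach a nominal Month 24 visit while the study was still open.

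A reader might infer that late harms go wholly unrecorded, or that long-term safety cannot be described at all. The documents do not support that. Section 7.3 keeps a route for possibly related SAEs after the end of the study. JointStem subjects have scheduled AE recording through Month 12. The examination, MRI and treatment records at Month 24 may reveal some harms indirectly, though not with the onset, severity and relationship that sections 7.2 and 7.2.1 ask for.

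A reader might also infer that the Month 24 score comparison is distorted because controls have 18 months free of treatment limits against 12 for JointStem. Section 3.5.7 does not say so. It opens pain medication after Month 6 without distinguishing arms, and its limit on other treatments up to the 12-month visit names no arm either. Treatment history is already among the data that "will be analyzed between treatment groups to see any long-term effects of JointStem". Nor could the comparison be repeated with subjects who had other treatment counted as not improved, since the plan defines no cut-off for improvement on the scales.

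Finally, recall over 12 to 18 months at a voluntary visit will be incomplete. That is true, and it belongs in the report as a limitation. An incomplete prompted record is still better than none.

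**Conclusion.** The point holds in a limited form. Month 24 has no AE item anywhere it is defined, and this does not fit the section 3.6.3 rule as worded. What lacks scheduled capture is non-serious AEs and SAEs not judged possibly related. The 58% figure assumes that all 30 planned subjects attend on the nominal date, and it measures time without scheduled AE questions, not events lost. Possibly related SAEs keep a reporting route after the end of the study, but it needs the site to learn of the event and to judge it related.

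This is a minor point. It leaves the Month 6 efficacy analyses untouched. It deserves action because the visit is already planned and a small change would add safety information.

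**What to change.** - Mark AE recording in the Month 24 column of the protocol schedule, and add AEs and SAEs since the last visit to sections 3.6.4 and 4.2.11.
- In the SAP, add the Month 24 visit and list these events by arm, separately from the TEAE tables. Because the end of study is fixed by the last subject, state the TEAE cut-off for each subject so that no event falls into both. Note beside the listing the look-back periods (12 months for JointStem, 18 for control) and the limits of recall, and do not compare raw counts between arms as if the periods were equal.
- Reconcile protocol sections 3.5.3, 3.6.3 and 7.3 on how long AEs and SAEs are collected, including the Month 3 SAE sentence against the sentences on follow-up and on events after the end of the study.

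The cost is one form at an existing visit, one listing, the protocol wording and a minor SAP amendment. The drawback is imperfect recall.
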